Applicable sections: Section 4.1.2 (exclusion criterion 12) and Section 7.4.

CSL Behring

CSL312_3001

CSL312 (Factor XIIa Inhibitor Monoclonal Antibody)

Administrative Amendment #1

**LIST OF PERSONNEL AND ORGANIZATIONS RESPONSIBLE FOR CONDUCT
OF THE STUDY**

A list of personnel and organizations responsible for the conduct of the study will be supplied to study sites as part of the Investigator's Study File. This list will be updated by CSL Behring, LLC (or delegate) and provided to the study sites as needed.

REVISION HISTORY

Date	Version	Summary of Changes
04 August 2020	Original	Not applicable

Clinical Study Protocol Synopsis

Title	A Multicenter, Double-Blind, Randomized, Placebo-Controlled, Parallel-Arm Study to Investigate the Efficacy and Safety of Subcutaneous Administration of CSL312 (garadacimab) in the Prophylactic Treatment of Hereditary Angioedema
Study Number	CSL312_3001
Sponsor	CSL Behring, LLC
Development Phase	3
Study Product	CSL312 (Factor XIIa Inhibitor Monoclonal Antibody)
Indication	Prophylaxis to prevent hereditary angioedema (HAE) attacks
Study Summary and Overview	
This is a multicenter, double-blind, randomized, placebo-controlled, parallel-arm, phase 3 study to investigate the efficacy and safety of 200 mg CSL312 (also known as garadacimab) administered subcutaneously (SC) once a month for the prophylaxis to prevent HAE attacks in adolescent (12 to 17 years, inclusive) and adult subjects with C1-esterase inhibitor (C1-INH) HAE. This study will be conducted globally.
 
Following informed consent, subjects will undergo a Screening Period of up to 1 month to determine eligibility for enrollment into the study. Screened subjects who meet all the inclusion and none of the exclusion criteria will enter a Run-in Period to confirm the required baseline HAE attack rate of \geq 1 attack per month. Subjects must complete at least 1 month of the Run-in Period. Additionally, subjects must experience at least 2 HAE attacks during the Run-In Period to be eligible to enter the Treatment Period. Subjects who experience at least 2 attacks during the required first month of the Run-In Period may enter the Treatment Period if they also meet all other criteria as stated in Section 4.1.3.

Subjects who do not meet the screening criteria for entering the Run-in Period within 30 days may be able to rescreen with confirmation from the sponsor. Subjects who do not meet the minimum HAE attack rate during the Run-in Period and / or all other criteria for entering the Treatment Period will be considered Run-in failures and will not be allowed to rescreen.

Eligible subjects will be randomized 3:2 to either the CSL312 Active Arm (CSL312 SC once a month) or the Placebo Arm. The duration of treatment is 6 months. Randomization will take age (\leq 17 years, $>$ 17 years) and, for adults, baseline attack rate observed during the Run-in Period (1 to $<$ 3 attacks / month, and \geq 3 attacks / month) into account.

Following the Treatment Period, subjects will either enter a 2-month Follow-up Period (ie, 3 months after last investigational product administration) or may roll-over into an open-label phase 3b study (CSL312_3002).

Primary Objective(s)	The primary objective of this study is to evaluate the efficacy of SC administration of CSL312 as prophylaxis to prevent HAE attacks in subjects with HAE.
Primary Endpoint(s)	The primary endpoint is the time-normalized number of HAE attacks during treatment from Day 1 through Day 182.
Secondary Objective(s)	
The secondary objectives of the study are:
 
1. To characterize the clinical efficacy of SC CSL312 in the prophylactic treatment of HAE.2. To evaluate the safety of SC CSL312 in the prophylactic treatment of HAE.

Secondary Endpoint(s)	
The secondary endpoints of the study are:
 
• The reduction in the attack rate during the Treatment Period compared to the Run-in Period.• The time-normalized number of HAE attacks requiring on-demand treatment.• The time-normalized number of moderate and / or severe HAE attacks.• The time-normalized number of HAE attacks at various time points during the treatment period.• Subject Global Assessment of Response to Treatment (SGART).• Adverse events (AEs).• Adverse events of special interest (AESIs).• Serious adverse events (SAEs).• CSL312 induced anti-CSL312 antibodies.• Clinically significant abnormalities in laboratory assessments (ie, laboratory abnormalities reported as AEs).
Study Duration	
The duration of the study for an individual subject is expected to be approximately 7 to 11 months. This estimation is based on:
 
• A Screening Period of up to 1 month.• A Run-in Period of 1 to 2 months (Run-in can occur on the same day as Screening).• A 6-month Treatment Period.• A Follow-up Period of 2 months (ie, 3 months after last investigational product administration). 
The overall study duration (ie, first subject's Screening Visit to last subject's End of Study Visit) will be approximately 19 months.

Number of Subjects	
This study will target to randomize 60 subjects with C1-INH HAE type 1 or type 2 to be included into the Treatment Period. The approximate sample size includes a targeted number of 5 adolescent subjects 12 to 17 (inclusive) years of age.

**Study Population
and Main Criteria
for Eligibility**

The main eligibility criteria to enter the study are:

1. Capable of providing written informed consent and willing and able to adhere to all protocol requirements and / or the subject's parent(s) or legally acceptable representative(s) capable of providing written informed consent / assent as appropriate.
2. Male or female.
3. Aged ≥ 12 years at the time of providing written informed consent or assent for minors.
4. Diagnosed with clinically confirmed C1-INH HAE
 - a. Documented clinical history consistent with HAE (subcutaneous or mucosal, nonpruritic swelling episodes without accompanying urticaria), and
 - b. C1-INH antigen and/or functional activity $\leq 50\%$ of normal as documented in the subject's medical record, and
 - c. C4 antigen concentration below the lower limit of the reference range as documented in the subject's medical record.
5. Experienced ≥ 3 HAE attacks during the 3 months before Screening, as documented in the subject's medical record.

Note: For subjects taking any prophylactic HAE therapy during the 3 months before Screening, ≥ 3 HAE attacks may be documented over 3 consecutive months before commencing the prophylactic therapy.

**Study Product
Dose, Dosing
Regimen and
Administration**

Subjects randomized to the Active Arm will receive CSL312 SC once monthly for 6 months. The first dose of CSL312 will be a 400 mg loading dose administered SC as 2 separate injections on the same day at the study site (ie, Month 1). Subsequent doses of CSL312 will be 200 mg administered SC once monthly for 5 consecutive months (ie, Months 2 through 6).

**Comparator
Product, Dose,
Dosing Regimen
and Administration**

Subjects randomized to the Placebo Arm will receive volume-matched placebo. The first dose of placebo in the Placebo Arm will be volume-matched placebo administered SC as 2 separate injections (ie, Month 1). Subjects will then receive volume-matched placebo SC once a month for 5 consecutive months (ie, Months 2 through 6).

Efficacy Assessments	Efficacy will be assessed by the number of HAE attacks (per month and annualized) in subjects treated once monthly with either CSL312 (Active Arm) or placebo (Placebo Arm) during the efficacy evaluation period from Day 1 through Day 182 (6 months). Subjects will record relevant information in an electronic diary (eDiary).
Safety Assessments	Safety will be assessed by treatment-emergent adverse events (TEAEs), vital signs, physical examinations, hematology, biochemistry, urinalysis, coagulation parameters, and anti-drug antibodies.
Pharmacokinetics	Plasma samples will be collected for assessment of CSL312 concentrations.
Pharmacodynamics	Plasma samples will be collected for assessment of Factor XII (FXII) concentration and activated FXII (FXIIa)-mediated kallikrein activity.
Other Assessments	Quality of life data will be obtained using the Angioedema Quality of Life (AE-QoL) questionnaire, EuroQoL Group 5-Dimension 5-Level (EQ-5D-5L) questionnaire, the Work Productivity and Activity Impairment: General Health (WPAI:GH) questionnaire, the Investigator Global Assessment of Response to Treatment (IGART), and the Subject Global Assessment of Response to Treatment (SGART).

Statistical Analyses Forty subjects with C1-INH HAE type 1 and 2 completing 6 months of treatment are needed to achieve a power of approximately 90% for a two-sided Wilcoxon Test (alpha of 5%). Subjects will be randomized to the Active Arm and the Placebo Arm with a ratio of 3:2. An attack rate per month of 0.3125 for CSL312-treated subjects and of 1.3 for subjects receiving placebo are assumed. The monthly attack rates of placebo and of CSL312 are assumed to be Poisson distributed.

It is targeted to randomize approximately 5 adolescents into the treatment period with a randomization ratio of 3:2 (active:placebo). To allow for sufficient safety data, increase the likelihood of adolescents entering the study, and to have at least 40 subjects reaching the end of the study, an additional 20 subjects are planned for randomization.

The primary estimand, in line with the primary interest of the study, follows the treatment policy strategy and is described as follows:

- Population: the target patient population defined by eligibility criteria and who were randomized (intent-to-treat [ITT]).
- Variable: time-normalized number of HAE attacks during treatment from Day 1 through Day 182.
- Intercurrent events: The occurrence of an intercurrent event is irrelevant. All observed values will be used regardless of occurrence of any of the following intercurrent events:
 - administration of on-demand medication in addition to prophylactic treatment with CSL312
 - non-compliance to treatment
 - early termination
- Population-level summary: median time-normalized number of HAE attacks per month during treatment from Day 1 through Day 182 by treatment.

The primary endpoint will be analyzed using the ITT and Per Protocol (PP) Populations. The ITT population will be used as the primary analysis and the PP will be used as the secondary analysis.

The primary endpoint “time-normalized number of HAE attacks per month during treatment from Day 1 through Day 182” is calculated per subject as:

[the number of HAE attacks / length of subject treatment in days] * 30.4375

where the length of subject treatment is calculated as:

[the date of Study Visit Day 182 or the date of study discontinuation [whatever is first]– the date of Study Visits Day 1 +1].

To test for a difference in the primary efficacy endpoint between CSL312 and placebo, a comparison of the time-normalized numbers of HAE attacks in the 6 months of the Active Arm and in the 6-month Placebo Arm period will be performed by using a two-sided Wilcoxon Test (alpha = 5%).

The time-normalized number of HAE attacks per month and annualized will be summarized descriptively for the 6 months of the Active Arm and the 6-month Placebo Arm period by median and mean with corresponding 95% confidence intervals (CIs).

Schedule of Assessments: Screening and Run-in Period (All Subjects)

Study Period	Screening	Run-in Period ^B				
	Visit Day	-30 to -1 ^A	1	15	30	45
Visit Window (Days)			± 4	± 4	± 4	± 4
Informed consent / IRT registration ^D	X					
Eligibility criteria ^E	X	X				
Study center visit	X					
Telephone contact		X ^F	X	X	X	X
Relevant medical history ^G	X					
Demographics	X					
Pregnancy test (at study site) ^H	X					
Physical examination ^I	X					
Vital signs including height and body weight	X					
Urine collection for urinalysis (central lab)	X					
Blood Draws (central lab)	Hematology / Biochemistry / Coagulation	X				
	C1-INH and C4 ^J	X				
Individual acute action plan ^K	X					
eDiary training	X	X ^L				
Open eDiary access		X				
eDiary completion by subject		↔				
Review eDiary data and assess / document HAE attacks ^M			X	X	X	X
Close eDiary access and collect device ^N						X
Confirm access to on-demand HAE medication ^O		X	X	X	X	X
Prior / concomitant medications and therapies	↔					
Adverse events	↔					

Abbreviations: C1-INH = C1-esterase inhibitor; C4 = complement C4; CSL = CSL Behring; eDiary = electronic diary; HAE = hereditary angioedema; IRT = interactive response technology

Footnotes to the Schedule of Assessments: Screening and Run-in Period [All Subjects]

- A: The first day of the Run-in Period may occur on the same day as the Screening Visit for subjects meeting the eligibility criteria for the Run-in Period.
- B: Subjects must complete at least 1 month of the Run-in Period. Subjects may enter the Treatment Period once they experience at least 2 HAE attacks.
- C: If a subject is unable to enter the Treatment Period after Day 60, then CSL approval is required for the subject to enter the Treatment Period. Day 60 will conclude the study for a subject who has entered the Run-in Period and is subsequently not eligible to be randomized. Eligible subjects will proceed to the Day 1 visit of the Treatment Period.
- D: Written informed consent must be provided before any study-specific assessments or procedures are performed.
- E: Eligibility to be confirmed before any study assessments are performed. The start of the Run-in Period should be recorded in the IRT after reconfirming eligibility.
- F: Telephone contact is not applicable when the first day of the Run-in Period occurs on same day as the Screening Visit.
- G: Include C1-INH functional activity and antigen, and C4 antigen concentration history, recording of overall health within the 6 months before Screening; HAE history including type, age of diagnosis, medical records to support diagnosis (ie, attack frequency, history of laryngeal attacks, prior prophylaxis therapy and on-demand treatment medication) within the 6 months before Screening, and contraception method (for female subjects of childbearing potential only).
- H: A urine test for beta-human chorionic gonadotropin will be performed for sexually active women of childbearing potential (only). A serum pregnancy test will be performed by the site if the urine result is inconclusive.
- I: A physical examination will be conducted per the investigator's standard procedure and will also include assessment of unilateral pain and / or swelling of the lower extremities for the purpose of screening for deep vein thrombosis.
- J: Blood sample for C1-INH functional activity and antigen, and C4 antigen concentration will be collected during the Screening Period for confirmation of historical laboratory values contained in the subject's medical record. If a subject requires the use of on-demand medication to treat an HAE attack within 120 hours (ie, 5 days after C1-INH administration) before Screening, then that subject may return to the study site within the first 2 weeks of the Run-in Period for a second blood draw to assess C1-INH antigen concentration and functional activity, and C4 antigen concentration.
- K: An individual acute treatment plan will be developed by the investigator to ensure that participating subjects are capable of managing their HAE attacks during the study and confirmation of subject's access to on-demand HAE medication to treat HAE attacks. The action plan will be reviewed with subjects.
- L: Repeat remote training is required if 30 days have elapsed between training at the Screening Visit
- M: Refer to [Appendix 2](#) for instructions on HAE attack documentation and assessment.
- N: Access to the eDiary should be closed at the Day 60 Telephone Contact for subjects who are not eligible to enter the Treatment Period. eDiary should be returned.
- O: Berinert is the suggested on-demand medication for use during this study. However, subjects may use the on-demand medication of their choice to treat HAE attacks experienced during the study if that medication has previously been shown to be effective.

Schedule of Assessments: Treatment Period

Study Period	Treatment Period ^A						End of Treatment Period ^{B,C}	Follow-up ^D /Final Visit
	1	2	3	4	5	6		
Month	1	2	3	4	5	6	7	9
Visit Day / Dose Number	1/1	31/2	61/3	91/4	121/5	151/6	182	242
Visit Window (Days)	NA	±4d	±4d	±4d	±4d	±4d	±4d	-14d
Study center visit	X	X	X	X	X	X	X	
Confirm eligibility for Treatment Period ^E	X							
IRT treatment arm assignment	X							
Pregnancy test (at study site) ^{F,H}	X	X	X	X	X	X	X	
Physical examination ^{G,H} , vital signs, and body weight ^H	X	X	X	X	X	X	X	
12-lead ECG ^I	X						X	
Urine collection for urinalysis (central lab)	X ^J			X			X	
Blood Draws (central lab) ^{H,P}	Hematology/Biochemistry / Coagulation		X ^J		X			X
	Retention sample for HAE biomarkers (adults only) ^K		X	X	X	X	X	X
	PK / PD ^L		X	X	X	X	X	X
	Immunogenicity ^M		X		X		X	
Concomitant medications and therapies	↔↔↔↔↔↔↔↔							
Adverse events	↔↔↔↔↔↔↔↔							
PRO / eCOA tablet training ^N	X							
AE-QoL (subjects ≥ 18 years) and WPAI-GH (subjects ≥ 16 yrs)	X	X	X	X	X	X	X	
EQ-5D-5L	X			X			X	
SGART and IGART ^O				X			X	
Review eDiary data (entered by subject) and assess / document HAE attacks	X	X	X	X	X	X	X	X ^P
eDiary deactivation							X ^Q	X ^P
Confirm access to on-demand HAE medication ^R	X	X	X	X	X	X	X	
IRT investigational product kit assignment	X	X	X	X	X	X		

SC administration of investigational product	X ^S	X ^T						
Investigational product accountability	X	X	X	X	X	X		
Offer subject option to enroll in Study CSL312_3002						X ^B		

Abbreviations: AE-QoL = Angioedema Quality of Life; C1-INH = C1-esterase inhibitor; C4 = complement C4; ECG = electrocardiogram; eCOA = electronic clinical outcomes assessment; EQ-5D-5L = EuroQoL Group 5-Dimension 5-Level; FXII = Factor XII; FXIIa = activated Factor XII; HAE = hereditary angioedema; ICF = informed consent form; IGART = Investigator's Global Assessment of Response to Therapy; IRT = interactive response technology; PK / PD = pharmacokinetic / pharmacodynamics; PRO = patient reported outcomes; SC = subcutaneous; SGART = Subject's Global Assessment of Response to Therapy; WPAI:GH = Work Productivity and Activity Impairment: General Health; yrs = years.

Footnotes to the Schedule of Assessments: Treatment Period [All Subjects]

- A: Treatment Period Visits have \pm 4 day window, with a maximum of 33 days between any 2 consecutive doses.
- B: The Day 182 End of Treatment Period Visit corresponds to the first day of the open-label phase 3b study for subjects rolling-over into Study CSL312_3002. Subjects will enter Study CSL312_3002 after completing the Day 182 assessments and signing the ICF for Study CSL312_3002. Subjects not entering Study CSL312_3002 will be required to complete the Day 242 study visits after completing the Day 182 assessments.
- C: Subjects who terminate early from the study (ie, before Day 182) will undergo the assessments specified for the End of Treatment Visit (Day 182), if possible.
- D: Subjects who do not enter Study CSL312_3002 are required to complete the Follow-up Visit. The in-person Follow-up Visit may be waived in place of a telephone contact during which information about adverse events and concomitant therapies / medications will be collected. If the Follow-up Visit is conducted as an in-person visit, then a blood draw for assessment of PK / PD and immunogenicity should occur, as well as collection of information about adverse events, concomitant therapies / medications.
- E: Subjects are eligible to exit in the Run-in Period and enter the Treatment Period after completing at least 1 month of the Run-in Period and experiencing at least 2 HAE attacks. C1-INH functional activity and antigen, and C4 antigen concentration levels should be confirmed before randomization into the Treatment Period. Eligibility to be confirmed before randomization and any study assessments are performed.
- F: The urine test for beta-human chorionic gonadotropin will be performed for sexually active women of childbearing potential (only). A serum pregnancy test will be performed by the site if urine result is inconclusive.
- G: A physical examination will be conducted per the investigator's standard procedure and will also include assessment of unilateral pain and / or swelling of the lower extremities for the purpose of screening for deep vein thrombosis.
- H: At visits, administration of investigational product will occur after physical examinations, vital signs, body weight, and pregnancy tests have been completed.
- I: Standard 12-lead ECGs will be performed.
- J: Assessments may be omitted if Screening / Run-in Period assessments occurred within the previous 3 months.
- K: Blood samples for potential future assessment of HAE biomarkers will be obtained during the Treatment Period. These samples will be stored for potential testing of HAE biomarkers and will be destroyed within 5 years after completion of the study or used for future research on HAE. These samples will not be collected in adolescents.
- L: Blood sample for PK includes CSL312 concentration and blood sample for PD includes FXII concentration and FXIIa-mediated kallikrein activity.
- M: Blood sample for binding antibodies (inhibitory and non-inhibitory) specific to FXIIa inhibitor monoclonal antibody (anti-CSL312).

N: The following patient related outcomes will be entered at specified study site visits before any other interaction with the subject about their health status and before review of the electronic diary: AE-QoL, EQ-5D-5L, WPAI:GH, and SGART.

O: Investigator completes IGART in RAVE. Subjects complete SGART.

P: Only applicable for subjects not rolling over to Study CSL312_3002.

Q: The eDiary will be collected and deactivated on Day 182 for subjects rolling over to Study CSL312_3002 and on Day 242 for all other subjects. For subjects who terminate the study early, the eDiary should be deactivated and collected either on date of early termination or at the Follow-up Visit as applicable. If the Follow-up Visit is conducted remotely, the device should be returned to the site.

R: Berinert is the suggested on-demand medication for use during this study. Subjects may use the on-demand medication of their choice to treat HAE attacks experienced during the study if that medication has previously been shown to be effective.

S: The first dose of investigational product will be a loading dose consisting of either 2 SC injections of 200 mg CSL312 each for a total of 400 mg CSL312 (Active Arm) or 2 SC injections of volume-matched placebo (Placebo Arm) administered by the investigator or delegate at the study site.

T: Investigational product administration consisting of either one 200 mg CSL312 SC injection (Active Arm) or one SC injection of volume-matched placebo (Placebo Arm) may be self-administered by the subject under the supervision of the investigator or delegate at the study site.

Table of Contents

Schedule of Assessments: Screening and Run-in Period (All Subjects)	11
Schedule of Assessments: Treatment Period	13
Table of Contents	16
List of Abbreviations	22
List of Conventions	24
1 Introduction	25
1.1 Background	25
1.1.1 Factor XII	25
1.1.2 Factor XII and the Kallikrein-kinin Pathway	25
1.1.3 Background of Disease	25
1.1.4 Background on CSL312 and Rationale for Treatment of Hereditary Angioedema	27
1.1.5 Unmet Medical Need	28
1.2 Information on CSL312	29
1.2.1 Overview	29
1.2.2 Nonclinical Evaluation	29
1.2.3 Clinical Experience	29
1.3 Study Overview	31
1.4 Potential Risks and Benefits	31
2 Study Objectives and Endpoints	33
2.1 Primary Objective and Endpoint	33
2.1.1 Primary Efficacy Objective	33
2.1.2 Primary Efficacy Endpoint	33
2.2 Secondary Objectives and Endpoints	33
2.2.1 Secondary Objectives	33
2.2.2 Secondary Endpoints	34

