Note: All female subjects are assumed to be of childbearing potential except:

- Subjects aged > 60 years.

- Subjects aged 45 to 60 years (inclusive) with amenorrhea for \geq 1 year with documented evidence of follicle-stimulating hormone level $>$ 30 IU/L. If the follicle-stimulating hormone value is not available before randomization, a urine pregnancy test is required.
- Subjects who are surgically sterile for at least 3 months before providing informed consent.

Note: All male subjects are assumed fertile except subjects who are surgically sterile for at least 3 months before providing informed consent

13. Pregnant, breastfeeding, or not willing to cease breastfeeding.
14. Involved in the planning and / or conduct of the study (applies to CSL staff, staff at the study site, and third-party vendors).

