8.1.1 Demographics and Safety Assessments

Subject demographics and safety assessments to be conducted during this study are provided in [Table 4](#). Clinical laboratory assessments are to be performed at time points as detailed in the [Schedule of Assessments: Screening and Run-in Period \(All Subjects\)](#) and [Schedule of Assessments: Treatment Period](#). The time windows for each type of assessment are detailed in [Section 8.7.1](#).

Table 4 Study Procedures: Demographics and Safety Assessments

Assessment	Description		
Demographics	Year of birth / age	Sex	Race and ethnicity
Medical history	
Relevant medical history within the 6 months before Screening with respect to the overall health of the subject
 
 • Medical history of HAE: 
 ◦ type 1 or type 2 ◦ age of diagnosis ◦ any history of laryngeal attacks ◦ family history of HAE • Lab values C1-INH functional activity and antigen / C4 antigen concentration • medical records to support diagnosis • HAE attacks in the last 3 months 
 ◦ If on prophylactic therapy 3 months prior to screening, collect history of number of HAE attacks 3 months prior to the start of prophylactic therapy • Prior prophylaxis therapy and on-demand treatment medication 3 months prior to screening • Contraception method 
Prior (within 6 months before Screening) / concomitant medications and therapies
		
Pregnancy test^a	Urine test for Choriogonadotropin Beta (beta-human chorionic gonadotropin), for women of childbearing potential		
Physical examination	As per the investigator's standard procedure, including assessment of unilateral pain and / or swelling of the lower extremities for the purpose of screening for deep vein thrombosis		
Adverse events	
Evaluation of all adverse events (eg, causality/relatedness, severity, seriousness)
 
Adverse events of special interest:
 
 • Abnormal bleeding events • Thromboembolic events • Severe hypersensitivity including anaphylaxis 		
Vital signs	Blood pressure (systolic and diastolic)	Respiratory rate	
	Pulse rate	Temperature	Height and body weight
Cardiac function test	12-lead electrocardiogram		

Urinalysis^b	Bilirubin Glucose Nitrite Specific gravity	Occult blood Ketones pH Urobilinogen	Erythrocytes Leukocyte esterase Protein

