8.7.2 Screening Visit

All subjects (or the subject's authorized representative) must provide written informed consent before any study-specific assessments or procedures are performed. Written informed consent is not required for assessments or procedures performed according to standard of care (eg, for diagnosis or treatment); results from such assessments may be used in the determination of study eligibility. Subjects will be allowed to be rescreened (see [Section 4.2](#)).

A screening examination should be performed within 30 days before the start of the Run-in Period.

The following procedures will be conducted and documented at the Screening Visit:

- Obtain written informed consent and register the subject via the IRT.
- Review inclusion and exclusion criteria.
- Obtain relevant medical history including overall health for at least the 6 months before the Screening Visit, HAE history before Screening, and contraception method (for females of childbearing potential only).
- Record subject demographics.
- Collect urine for pregnancy test (for sexually active women of childbearing potential).
- Perform physical examination.
- Record vital signs, including height and body weight.
- Collect urine for urinalysis.
- Collect blood for:

- Hematology
- Biochemistry
- Coagulation
- C1-INH functional activity and antigen, and C4 antigen concentration for confirmation of historical laboratory values contained in the subject's medical record.
- Develop an individual acute action plan, including assessment of subject's ability to manage HAE attacks and confirmation of subject's access to on-demand HAE medication to treat HAE attacks.
- Perform eDiary training
- Record prior and concomitant medications and therapies (type, dose, route, date, and time) in the last 6 months.
- Begin to monitor AEs.

Re-screening: If a potential subject is not eligible for entry into the Run-in Period within 30 days after providing informed consent, then the subjects may re-consent and may be screened again (for a maximum of 2 Screening Periods per subject) after consultation with CSL. In the event that a potential subject is screened twice, all Screening assessments must be repeated during the second Screening Period. If the subject is not eligible for the study (ie, the subject is a Screen Failure), all eligibility criteria that are not met must be recorded in IRT.

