8.7.4.2 Treatment Period: Visit Days 31, 61, 121, and 151 (\pm 4 days)

The following procedures will be conducted at the Day 61 and Day 151 (\pm 4 days) site visits:

- Collect urine for pregnancy test (for women of childbearing potential and sexually active).
- Perform physical examination.
- Record vital signs and body weight.
- Collection of blood to assess:
 - PK / PD.
 - HAE biomarkers (retention sample) (adults only).
- Record concomitant medications and therapies (type, dose, route, date, and time).
- Record AEs.
- Subject to complete:
 - AE-QoL (subjects \geq 18 years).
 - WPAI:GH (subjects \geq 16 years).
- eDiary completion by subject.
- Review eDiary data, including investigator assessment of HAE symptoms and documentation of HAE attacks.
- Confirm access to on-demand HAE medication.
- Obtain investigational product kit assignment in IRT.
- Subcutaneous administration of investigational product by subject under supervision (after completion of pregnancy test, physical examination, vital signs, and blood sample collection).
- Accountability of investigational product.
- Offer subject option to enroll in Study CSL312_3002 (Day 151 only).

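### The schedule footnotes and visit lists limit the pregnancy test to sexually active women and Table 4 does not, so a woman judged not sexually active throughout may have none of 8 scheduled tests

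*Protocol*

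**What the plan says.** **With the limit.** Footnote H to the Screening and Run-in schedule: "A urine test for beta-human chorionic gonadotropin will be performed for sexually active women of childbearing potential (only". Footnote F to the Treatment Period schedule: "The urine test for beta-human chorionic gonadotropin will be performed for sexually active women of childbearing potential (only". The visit list in Section 8.7.2 has "Collect urine for pregnancy test (for sexually active women of childbearing potential", and the same line stands in 8.7.4.1 (Day 1) and 8.7.4.4 (Day 182). Section 8.7.4.2 has "Collect urine for pregnancy test (for women of childbearing potential and sexually active", repeated in 8.7.4.3 (Day 91).

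**Without the limit.** Table 4 in Section 8.1.1 gives "Urine test for Choriogonadotropin Beta (beta-human chorionic gonadotropin), for women of childbearing potential". Table 6 in Section 8.7.1 puts the pregnancy test before injection on the same day. Footnote H of the Treatment Period schedule (a different footnote from the Screening one) puts dosing after the test. Neither mentions sexual activity.

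**What the test protects.** Pregnancy is exclusion criterion 13 in Section 4.1.2, and Section 9.6.6 makes it a mandatory reason to stop investigational product. Section 7.4 accepts abstinence as contraception where it is the woman's preferred and usual lifestyle.

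**One separate rule.** In the note to criterion 12, for women aged 45 to 60 with amenorrhea: "If the follicle-stimulating hormone value is not available before randomization, a urine pregnancy test is required". That rule does not depend on sexual activity.

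**The concern.** Two instructions are in force, and they disagree about the same woman. If she is of childbearing potential and judged not sexually active, one set of texts exempts her from every scheduled test and the other requires all of them.

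On the exempting reading, an exclusion and a mandatory stop have no scheduled test behind them for her. If she relies on abstinence, one self-report serves both as her contraception and as the reason not to test her. If that report is wrong, or the site misjudges her status, both protections fail together.

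I found no text that says who judges sexual activity. The reproductive listing in SAP Section 9.3 covers childbearing potential, birth control method and pregnancy test details, but not sexual activity. It would therefore not show directly whether a woman without a test was exempt or had been missed.

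**Working it through.** No formula applies. The check is a count and a comparison of texts.

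**Reproducing the plan's own figure.** SAP Section 10.6 plans 6 injections, with the two-syringe loading dose counted as one. The Treatment Period schedule has doses on Days 1, 31, 61, 91, 121 and 151, which is 6. The figures agree.

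**Scheduled pregnancy tests.**
- Screening and Run-in schedule: 1 (Screening).
- Treatment Period schedule: 7 (Days 1, 31, 61, 91, 121, 151, 182).
- Total: 1 + 7 = 8. By type: 1 at Screening + 6 at dosing visits + 1 at Day 182 = 8.

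The heading of Section 8.7.4.2 names Days 31, 61, 121 and 151, while its opening sentence names only Days 61 and 151. The schedule marks the test at all four, so I use 8.

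**Who is tested, by source.**

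| Source | Limited to sexually active? |
|---|---|
| Screening footnote H | Yes, with *only* |
| Treatment footnote F | Yes, with *only* |
| 8.7.2 Screening | Yes |
| 8.7.4.1 Day 1 | Yes |
| 8.7.4.2 Days 31, 61, 121, 151 | Yes |
| 8.7.4.3 Day 91 | Yes |
| 8.7.4.4 Day 182 | Yes |
| 8.1.1 Table 4 | No |
| 8.7.1 Table 6 | Silent (timing only) |
| Treatment footnote H | Silent (order only) |

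Places with the limit: 2 footnotes + 5 visit lists = 7.

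**Result for a woman of childbearing potential judged not sexually active at every visit.**
- Footnotes and visit lists: 0 of 8 scheduled tests, with all 6 doses given untested.
- Table 4: 8 of 8.
- The FSH rule could add one test for some women aged 45 to 60. It is not one of the 8.

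**A woman whose status changes.** The condition is attached to each visit, so I read it as applied afresh each time. If she reports a change between two doses, she is tested at the next dosing visit. Footnote A of the Treatment Period schedule caps that gap: "with a maximum of 33 days between any 2 consecutive doses". The gap that remains is the woman judged not sexually active throughout.

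**The case against.** The strongest reply is that this is a deliberate rule, stated alike in seven places and twice with *only*. Section 8.1 sends timing and frequency to the schedules, whose footnotes carry the limit, so a site working from the visit lists meets one consistent instruction. Table 4 is then one loosely worded cell, and adding two words to it would remove the mismatch. A woman who is truly not sexually active is not at risk, and Section 7.4 rejects periodic abstinence and withdrawal.

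Other safeguards also apply to her: exclusions 11 and 12, the contraception method recorded at Screening, the visit examinations, further assessments at the investigator's discretion (Section 8.1), and the duty in Section 9.6.6 to report a pregnancy at once.

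Much of this stands. The restriction does look deliberate, and the restricted reading is the likelier one in practice. Table 6 and Treatment footnote H do not settle who is tested, because they deal with timing and order. But reading the conflict in favor of the footnotes leaves the gap in place. The other safeguards rest largely on self-report, and none requires a test. Discretion needs a clinical prompt, which a misreport does not give. No reason for the exemption is stated.

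**Conclusion.** The mismatch is real: 0 or 8 of 8 scheduled tests for the same woman, depending on the text followed. Resolving it toward Table 4 would be a cheap safety improvement. The case rests on one assumption, that some women's status may be misreported or misjudged. The documents give no number of women, no share who are not sexually active and no misreporting rate, so the risk cannot be sized and may be small. Sample size, power and analysis are untouched.

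A reader might infer more than the documents support:

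- **That pregnancies will be missed, with a known exposure.** The full six-dose regimen is simply what any subject receives. It does not measure added risk.
- **That seven tests guard a dose because seven come before one.** The Screening test comes at least a month before Day 1, because the Run-in Period lasts at least 1 month. Only six tests fall at dosing visits.
- **That the protocol defines childbearing potential inconsistently.** The criterion 12 note and the Section 7.4 footnote do describe menopause differently. But Administrative Amendment #1 applies to exactly those two sections and its content is not available, so no conclusion can be drawn.
- **That women aged 45 to 60 without an FSH value belong on the full test schedule.** The note can equally mean one test in place of the missing value, and the same amendment applies.

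**What to change.** Delete the sexual-activity condition from Screening footnote H, Treatment footnote F and the pregnancy-test lines in Sections 8.7.2 and 8.7.4.1 to 8.7.4.4. Delete *only* from the two footnotes. All women of childbearing potential are then tested as in Table 4.

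Add an explicit exception for girls before menarche, in Table 4 as well as in the footnotes. The trial enrolls from age 12, and the criterion 12 note as available here begins "All female subjects are assumed to be of childbearing potential except" and lists no such exception. Without one, the change would put a premenarchal girl on the full test schedule.

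Adding the condition to Table 4 instead would make the texts agree but leave these women untested.

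The cost is wording in seven places plus the exception, and up to 8 extra on-site urine tests per affected woman, at visits already scheduled. Some of those tests would fall on adolescents, of whom about 5 of 60 subjects, both sexes together, are targeted.
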